13.2 Early Stopping Rule for Toxicities

The complications and adverse events will be closely monitored in this study. The hypothesized rate of having grade 4 or 5 non-hematologic, non-infectious toxicities for the approach is 5%. Enrollment will be stopped and the trial re-evaluated if the grade 4 or 5 toxicity rate shows signs to exceed 15%. This means enrollment will be stopped and the study re-evaluated if there are 3 patients with a non-hematologic, non-infectious grade 4-5 toxic event occurring through day 45 of the last treatment course out of the first 7 patients, 4 out of 18, 5 out of 29, 6 out of 40, and 7 patients at any time. Toxicities such as infections, including but not limited to pneumonia, bacteremia, cellulitis, and neutropenic fever, etc are known results of high risk MDS and will not be included as toxicities attributed to the study therapy. Assessment for toxicities will begin upon initiation of trial therapy and will conclude 2 weeks after last dose of study related treatment. These stopping rules of a statistical sequential probability ratio test designed for no more than 5% the probability of type I error and at least 80% statistical power.

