3.0 Study Design

This is a Phase II therapeutic trial combining Decitabine days 1-5 with oral Vorinostat twice daily days 6-15 followed by a single infusion of CD3-/CD19-enriched donor NK cells on day 17 and a short course of Interleukin-2 (IL-2) to facilitate NK cell survival and expansion. Two courses of treatment will be given separated by 6 - 8 weeks. Clinical response will be formally assessed 4 - 6 weeks after the 2nd course based on International Working Group (IWG) criteria;

however, a bone marrow evaluation will be done if the patient is taken off treatment prior to study completion. **The intent is to administer all treatment in the outpatient setting.**

The trial will use Simon's two-stage design. Fifteen patients will be enrolled in stage 1. If 6 or more of the patients achieve an objective clinical response (CR + PR + hematologic improvement (HI)), stage 2 will be activated and an additional 31 patients enrolled for a total of 46 evaluable patients. Considering a predicted dropout rate of 10% during the two courses of therapy, stage 1 will need a maximum of 17 patients or a maximum of 51 patients if the study proceeds to 2nd stage.

Research and related correlative studies will be done at baseline, between courses 1 and 2, and after completion of course 2 as per section 8.1.2.

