13.0 Statistical Considerations

13.1 Simon's Two-Stage Design and Sample Size

This is a single clinic Simon's optimum two-stage phase II clinical trial designed to determine the objective response rate (CR+PR+HI) after two courses of Decitabine and Vorinostat with haploidentical NK cells in patients with high risk MDS. The null hypothesis of the study is $P_{R0} \leq 0.30$ and alternative hypothesis is $P_{R1} \geq 0.50$. Based on this design and the assumption that the majority of patients will complete both cycles of therapy, a maximum of 46 evaluable patients will be used which is sufficient to maintain an overall type I error 5% while providing 80% statistical power.

In the first stage 15 patients will be enrolled, the trial will be terminated if 5 or fewer respond. If 6 patients respond, then the trial goes on to the second stage, and 31 more patients will be studied. If the total number responding is less than or equal to 18, then this approach will be deemed unworthy of further study.

Considering a predicted dropout rate of 10% during the two courses of therapy, in order to have 15 or 46 patients evaluable for the response rate, we will need a maximum of 17 patients (if the study is stopped by 1st stage) or 51 patients (if the study proceeds to 2nd stage).

Only patients completing both course 1 and 2 of planned therapy will be evaluable for response. However, all the patients with complete or partial treatment will be included in the evaluation for toxicities.

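### The toxicity stopping rule in Section 13.2 has about 71% power at a 15% toxicity rate within the planned 51 patients, not the stated 80% or more; the 5% type I error bound holds

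*Combined protocol and SAP*

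**What the plan says.** Section 13.2 takes 5% as the hypothesized rate of grade 4 or 5 non-hematologic, non-infectious toxicity. Enrolment is to stop for re-evaluation if "the grade 4 or 5 toxicity rate shows signs to exceed 15" percent. The operational rule is to stop "if there are 3 patients with a non-hematologic, non-infectious grade 4-5 toxic event" "out of the first 7 patients, 4 out of 18, 5 out of 29, 6 out of 40, and 7 patients at any time". The section says the rules come from a sequential probability ratio test (SPRT) "designed for no more than 5% the probability of type I error and at least 80% statistical power".

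The size of the trial is set in Section 13.1. After an allowance of 10% for dropout, "we will need a maximum of 17 patients (if the study is stopped by 1st stage) or 51 patients" if stage 2 opens; Section 3.0 gives the same maximum. Section 13.1 also states that "all the patients with complete or partial treatment will be included in the evaluation for toxicities", so every treated patient counts towards the rule, not only the 46 evaluable for response. For stage 1, "the trial will be terminated if 5 or fewer respond".

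**The concern.** An SPRT has its nominal error rates only if it may run until it reaches a decision. This trial cannot, because its maximum size is printed. Capping a test of this kind lowers the chance of crossing the upper line, both under the acceptable rate and under the rate of concern. One would therefore expect the type I error to be below 5% and the power to be below 80%; the question is by how much.

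This is the protocol's only numerical toxicity stopping rule, and the study is classed as high risk in Section 12.3. Those who judge whether patients are adequately protected will read the sentence in Section 13.2 as a property of the rule in this trial. If it is wrong, they believe a 15% rate would be missed at most 20% of the time when the true figure is higher.

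**Working it through.** **Inputs.** Acceptable rate p0 = 0.05, rate of concern p1 = 0.15, type I error α = 0.05, power 0.80 (β = 0.20), and thresholds 3 of 7, 4 of 18, 5 of 29, 6 of 40, then 7 (Section 13.2). Maximum treated 51, evaluable 46, stage 1 up to 17 treated (Section 13.1).

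**Step 1: reproduce the boundary.** The upper Wald line is k = h + s·n, with

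- D = ln[p1(1 − p0) / (p0(1 − p1))] = ln 3 + ln(0.95/0.85) = 1.2098
- h = ln[(1 − β)/α] / D = ln 16 / 1.2098 = 2.292
- s = ln(0.95/0.85) / D = 0.0919

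Setting k = 3, 4, 5, 6, 7 and solving n = (k − h)/s gives 7.70, 18.58, 29.46, 40.34 and 51.21. Rounded down, these are 7, 18, 29, 40 and 51. The first four are the printed sample sizes and the fifth equals the printed maximum. Section 13.2 does not say at which rate the 80% applies, but this match shows that it is 15%.

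**Step 2: exact crossing probabilities.** Let n be the number treated and k the number with at least one event. Starting from k = 0, each new patient moves k to k + 1 with probability p and leaves it unchanged with probability 1 − p. After each patient, any path with k at or above the threshold is removed and its probability added to the total. The threshold is 3 up to n = 7, 4 up to 18, 5 up to 29, 6 up to 40, and 7 thereafter.

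| Treated | 5% rate | 15% rate |
|---|---|---|
| 17 | 1.1% | 25.7% |
| 46 | 2.8% | 64.9% |
| 51 | 3.1% | 71.4% |
| 57 | 3.8% | 79.5% |
| 58 | 4.0% | 80.8% |

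A simulation of 400,000 trials gave 3.1% and 71.4% at 51 patients.

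**Step 3: size of the shortfall.** At 51 patients power is 80 − 71.4 = 8.6 points below the stated minimum, and the chance of missing a 15% rate is 100 − 71.4 = 28.6% rather than at most 20%. With 51 patients the rule reaches 80.0% only at a true rate of about 16.5%; at 20% it reaches 92.6%. To reach 80% at a 15% rate, 58 patients must be treated, 7 above the maximum. For 46 evaluable patients that means dropout of 1 − 46/58 = 20.7%, against the planned 10%.

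**Step 4: allow for the stage 1 futility stop.** The figures for 51 assume that stage 2 opens. The probability of at least 6 responders in 15 is 0.2784 at a 30% response rate and 0.8491 at 50%. If response and toxicity are independent and 17 are treated in stage 1, then at a 15% toxicity rate

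P(cross) = P17 + P(proceed) × (P51 − P17)

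- 30% response: 0.2565 + 0.2784 × (0.7138 − 0.2565) = 0.384
- 50% response: 0.2565 + 0.8491 × (0.7138 − 0.2565) = 0.645

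The corresponding values at a 5% toxicity rate are 1.6% and 2.8%. The probability of treating all 51 at a 15% rate without crossing is P(proceed) × (1 − 0.7138), which is 8.0% and 24.3%. Full enrolment is thus the case most favourable to the plan.

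**The case against.** The strongest reply is that the sentence describes a design target. A Wald SPRT of 5% against 15% with both its boundaries and no cap does deliver about 3.5% type I error and 81.0% power, so the statement is true of the test that is named. But the sentence attributes the error rates to the stopping rules themselves. Those rules print no lower boundary and operate under a printed maximum. What stands is that the fault lies in leaving out the effect of the cap, not in the derivation.

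Three assumptions can also be challenged.

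- *Counting unit.* Section 11.3 limits counting only within an episode or for concurrent events, so a patient might contribute twice. If, purely for illustration, 15% of affected patients did so, crossing at 51 would be 80.8% at a 15% rate but 8.8% at 5%: the power claim would then hold and the type I claim would fail. Section 13.2 sets its thresholds in patients, which supports counting each patient once.
- *Cap.* Section 6.2 replaces patients who discontinue and Section 7.5 replaces those given no IL-2, with no stated limit. Even so, Sections 3.0 and 13.1 call 51 a maximum, and it already includes the dropout allowance.
- *Timing of checks.* If the rule is examined only at 7, 18, 29 and 40 patients plus 7 events at any time, crossing within 17 patients falls to 0.4% and 7.6%, and the unconditional range at 15% becomes about 25% to 62%. The results at 46 and 51 do not change. That reading is strained, since 4 events in fewer than 18 patients already satisfy the second threshold, but the restated text should say that checking follows each patient.

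Finally, other oversight exists: stopping-rule events are reported individually (Sections 11.3 and 11.4) and the monitoring council receives quarterly reports (Section 12.3). This limits the consequence but does not make the stated power correct.

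**Conclusion.** The concern holds. The boundary is correctly derived and its type I error, 3.1% at 51 patients, is within the stated 5%. The claim of at least 80% power is not met within the planned size: it is 71.4% if all 51 are treated and lower if fewer are. Neither the conditional nor the unconditional figure reaches 80% at a 15% rate.

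This rests on one count per patient, all treated patients counting, immediate and complete ascertainment of events, and 51 as the limit. The unconditional figures also need independence of response and toxicity. It should be fixed because it misstates the protection given by the only numerical safety rule. The efficacy design is not affected.

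**What to change.** Replace the last sentence of Section 13.2 with the exact operating characteristics and their conditions, for example:

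> With each treated patient counted at most once and the boundary checked after every patient, the exact probability of crossing it if enrolment continues to the maximum of 51 treated patients (no stage 1 futility stop) is 3.1% if the true rate is 5% and 71% if it is 15%. Within the first 17 patients it is 1.1% and 26%.

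The sentence can still say that the thresholds were taken from the upper boundary of an SPRT with nominal 5% and 80%, provided the nominal and exact figures are kept apart. The cost is one sentence and a less favourable stated power. No change to thresholds, patient numbers or clinical management is proposed.

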13.3 Statistical Analysis Methods

Ninety-five percent confidence intervals for the response probability were calculated using methodology reported by Duffy and Santner.⁴⁰

The summary statistics including 95% confidence intervals for toxicity rate and proportion of patients who become transfusion independent will be calculated. The association of in vivo NK cell expansion, as defined as persistence of donor NK cell chimerism at day +8, (yes or no) with clinical response will be estimated by chi-square test. Kaplan- Meier method will be used to estimate 1- year survival from the date of treatment. Given that the majority of patients will go on to receive additional therapy with either ongoing hypomethylating agents versus stem cell transplant, the estimates of 1 year overall survival from the point of study enrollment, will only be partially attributable to the study therapy and thus a minor focus of our statistical analysis.

SAS 9.2 (Cary, NC, USA) will be used for statistical analyses.

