1.3 Correlative Laboratory Objectives

- Estimate the incidence of successful in vivo expansion of adoptively transferred haploidentical NK cells by NK cell persistence 2 weeks after infusion (Day 28)
- Monitor phenotypic and functional characteristics of natural killer cells and regulatory T cells in vivo

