Data from prior studies described in the section above suggest that those patients who achieved a remission were those who expanded NK cells in vivo. In the subsequent trial, MT2003-23, total body irradiation (TBI, 400 cGy) was added to cyclophosphamide and fludarabine (Cy/Flu) and we compared the rates of in vivo NK cell expansion (defined as 100 donor derived NK cells/ μ L blood) and leukemia clearance (defined as less

1% blasts in the bone marrow). Using this approach (n=13), successful in vivo expansion of adult donor NK cells was detected in 75% of patients with a mean of 606 ± 184 circulating donor derived NK cells/ μL blood 14 days after the adult NK cell infusion compared to a rate of only 10% in patients receiving Cy/Flu alone under the predecessor of this protocol, MT2004-25 (Figure 1). In vivo expansion correlated with leukemia clearance.

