8.1 Patient

8.1.1 Standard of Care and Investigational Treatment

	Pre-Treatment (within 28 days of treatment start)*	During each treatment course					4-6 weeks after 2 nd treatment course	Follow-up at Day 90, 180, 270, 360	
		Day 1 ¹	Day 5	Day 15 or 17	During IL-2 administration (Day 17-22)	Day 24, 31, 38, 45			
EVALUATIONS									
Written consent	X								
Medical history	X								
Disease Characteristics	X								
Pathology review of outside dx	X								
Transfusion History	X						X		
Concomitant meds	X	X					X		
Physical exam	X	X	X ⁶	X ⁶	X ⁶	X ⁶	X		
Vital signs	X	X		X					
Weight	X	X		X	3 x a week during IL-2	X			
Height	X								
ECOG Performance Status	X	X					X		
Survival Status								X ⁷	
LABORATORY									
CBC w/ diff ²	X	X	X	X	daily during IL-2	X	X		
Na, K, Cl, CO ₂ , BUN, creatinine, uric acid, phos, LDH, Mg	X	X	X	X		X			
ALT/AST, bili, total protein, albumin, alk phos	X	X		X		X			
Chest X-ray	X								
INR/PTT	X								
Pregnancy test ³	X								
HLA typing (low resolution)*	X								
Recipient Viral Serology	X								
ECHO/MUGA*	X								
Bone Marrow Bx/Asp ⁴	X ⁴					X ⁵	X ⁴		
Investigational TREATMENT									
Decitabine IV		Day 1-5							
Vorinostat PO			Day 6-15						
NK cell infusion (research)				Day 17					
IL-2 tiw for 3 doses (research)					X (start Day 17)				

* CBC, dff, CMP, chemistries within 14 days of study treatment start, HLA typing may be done at any time

- 1- Course 1 Day 1 evaluations need not be repeated if pre-study evaluations were done within 14 days of 1st treatment
- 2- CBC with diff weekly throughout all treatment with increased frequency as clinically indicated
- 3- Women of childbearing potential only; serum or urine
- 4- Bone marrow aspirate and biopsy with standard flow cytometry, conventional cytogenetics, and MDS/AML FISH panel will be conducted at study initiation and at the completion of the 2nd cycle for standard disease assessment or at time of study withdrawal if early termination.
- 5- Prior to course 2 ONLY in patients who enrolled in this study as a prior treatment failure per section 4.2.2 or any patient who is discontinuing study treatment after 1 course
- 6- Clinical assessments will occur at a minimum of weekly up until the NK cell infusion on Day +17 after which clinical assessments will occur daily until the day after the final IL-2 administration.
- 7- By record review, patient contact, etc.

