8.1.2 Patient – Research Related

	Before start of each chemo course	Before NK cell infusion	After each treatment course			
		Day 17	Day 24	Day 31	Day 38	Day 45 ³
Adverse Event Monitoring	Per section 11					
Chimerism – PB (unseparated)*	x		x	x ¹	x ¹	x ¹
60 ml of heparinized blood (green top tubes)*	x	x	x	x	x	x
10 ml of serum (red top tube)* for HAMA ²		x (post infusion)				
10 ml of serum (red top tube)*	x	x	x	x	x	x
BM 30 ml (heparinized)*	At the time of each bone marrow biopsy for clinical reasons					

1 – continue chimerism monitoring until they disappear

2 –draw sample in the event of a grade 4 infusion related toxicity occurs – refer to section 8.1.3

3 – the day 1 treatment course 2 sample may be eliminated if the patient is ready to start course 2 at day 45

*For the Cancer Center’s Translational Therapy Lab (TTL) – refer to section 8.3 for shipping instructions. (U of MN chimerism samples to be sent directly to the Molecular Diagnostics)

As recognized with novel therapies, as in this study, the timing of protocol directed research samples may miss important patient specific events. For this reason, up to 3 extra samples for a total of 180 ml of blood may be drawn at additional time points that are not specified above.

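### The NK expansion variable in section 13.3 is set at a day that, in the protocol's own numbering, precedes the infusion; read as post-infusion, it still conflicts with the two-week objective

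*Combined protocol and SAP*

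**What the plan says.** Section 1.2 lists the association between NK expansion and clinical response as a secondary objective, and section 9.0 repeats it as a secondary endpoint. Section 13.3 defines the exposure as "persistence of donor NK cell chimerism at day +8, (yes or no" and says that its association "with clinical response will be estimated by chi-square test".

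The correlative objective in section 1.3 judges successful expansion by "NK cell persistence 2 weeks after infusion (Day 28").

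The treatment schedule (section 3.0) is chemotherapy "followed by a single infusion of CD3-/CD19-enriched donor NK cells on day 17", in each of two courses. Footnote 6 to the calendar in section 8.1.1 describes weekly assessments "up until the NK cell infusion on Day +17". Section 8.0 uses the same plus-sign form for days +22 and +28.

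Section 8.1.2 schedules the test as "Chimerism – PB (unseparated"), drawn before each chemotherapy course and then on days 24, 31, 38 and 45. A footnote to the last three says that monitoring goes on until chimerism is gone.

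In the background (section 2.2), expansion in earlier AML work was "defined as 100 donor derived NK cells" per microliter of blood, with counts reported 14 days after infusion.

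**The concern.** An exposure variable needs a time origin, a day, a course, an assay and a rule for calling a result positive. Section 13.3 gives a day and a yes/no coding, but the day does not fit the calendar and the other elements are missing.

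Patients evaluable for response have had both courses (section 13.1), so each has two infusions and several post-infusion samples. With origin, course and cut-off all open, the exposure could be settled after responses are known. Two analysts working in good faith could also classify the same patients differently. The analysis is secondary, but it is the one that links the donor cells to the clinical result, so its definition should be fixed in advance.

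**Working it through.** **Inputs.** Infusion on day 17 (sections 3.0 and 7.0); donor apheresis on day 15 of course 1 (section 7.3); vorinostat on days 6 to 15 (section 7.2); chimerism before each course and on days 24, 31, 38 and 45 (section 8.1.2). Plus-sign days count from course start, since the infusion is itself called Day +17 (section 8.1.1, footnote 6). No section restarts the count at infusion.

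**The plan's own figure: two weeks after infusion = Day 28 (section 1.3).** It does not reproduce. 17 + 14 = 31. Day 28 is 28 − 17 = 11 days after infusion. The label would be right only if the infusion were on day 28 − 14 = 14.

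**Day +8 as a course day.** 8 − 17 = −9, so 9 days before infusion, in the vorinostat phase. In course 1 it is also 15 − 8 = 7 days before the donor cells are collected. No chimerism sample is scheduled.

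**Day +8 as a post-infusion day.** With the infusion as day 0: 17 + 8 = 25. With the infusion as day 1: 17 + 7 = 24.

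**Side by side.**

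| Reading | Course day | Days from infusion | Scheduled chimerism day? |
|---|---|---|---|
| Day +8, protocol numbering | 8 | −9 | No |
| Day +8, infusion = day 1 | 24 | +7 | Yes |
| Day +8, infusion = day 0 | 25 | +8 | No |
| Day 28, as labelled in 1.3 | 28 | +11 | No |
| Two weeks, as worded in 1.3 | 31 | +14 | Yes |

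No reading of section 13.3 agrees with either part of section 1.3. Of the post-infusion readings, two fall on nominal sampling days (24 and 31). With two courses, that leaves 2 × 2 = 4 sampled visits that could each be claimed as the planned one.

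**Visit windows.** Section 8.0 allows ±3 days after day +28, so the day 31 sample may be drawn from 31 − 3 = day 28. It gives ±1 day only up to day +22, so days 24 and 25 have no numeric window.

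**Assay and cut-off.** The variable concerns donor NK cells. The scheduled chimerism is on unseparated blood, which gives a donor fraction across all cell types. Section 13.3 does not say what level counts as yes.

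**The case against.** The best reply is that nobody could mean the persistence of cells not yet given, so day +8 must be post-infusion. Counting the infusion as day 1 puts it on course day 24, a scheduled chimerism day. The ±3-day window also lets the day 31 sample fall on day 28, and section 8.0 lets target days be altered where clinically appropriate. On this view the mismatch is loose wording in one secondary analysis of a single-arm trial.

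Much of this stands. Course day 24 is a workable reading and may be what was intended. But no text selects it, and it remains one week after infusion where section 1.3 asks for two. A visit window permits a sample on day 28; it does not make day 28 the two-week target. None of this supplies the course, the cut-off or the cell fraction.

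It can also be said that section 2.2's threshold of 100 cells per microliter describes earlier AML trials with different conditioning, and does not bind this trial. That is right.

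**Conclusion.** The point holds as a defect of definition. Section 13.3's day is 9 days before infusion in the protocol's numbering, or 7 to 8 days after it if the origin is the infusion. Section 1.3 gives two weeks (14 days) and Day 28 (11 days), which disagree with each other and with section 13.3. Course, positivity cut-off and cell fraction are unstated. The only assumption is that the infusion is on day 17, as the schedule says throughout.

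Three stronger readings are tempting, but the documents do not support them:

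- **That the plan means to measure before infusion.** An unstated time origin is far more likely.
- **That scoring persistence departs from this trial's own objective.** Section 1.3 itself judges expansion by persistence. The count threshold appears only in the background, and comparison with the rates cited there is not an objective.
- **That the choice of day costs a known amount of power.** Nothing in the documents links sampling day to the share of patients who would be positive, and no power is claimed for this analysis.

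The primary endpoint, the two-stage design and the sample size are unaffected.

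**What to change.** In sections 1.3 and 13.3, replace day +8 and Day 28 with one scheduled post-infusion visit in one named course, fixed before responses are analysed. Course 1 day 31 is a scheduled chimerism day, lies exactly 14 days after infusion and fits the two-week wording of section 1.3. Because the footnote in section 8.1.2 continues monitoring only until chimerism disappears, also say how a patient already negative on day 24, with no day 31 sample, is coded.

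State the cut-off for yes and the cell fraction tested, and align sections 1.3, 8.1.2 and 13.3.

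As an optional supportive analysis, report donor-derived NK cells per microliter, including the proportion at 100 or more. This requires a donor fraction measured within NK cells. The unseparated chimerism result cannot supply it, and no assay for it is described. It is feasible only if that fraction can be obtained from the heparinized blood already drawn at these visits.

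The visit, course, cut-off and coding rule cost only wording. If the variable is to stay NK-specific, testing a separated fraction may add laboratory work, but no extra visit.
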